Airway clearance is a strategy for treating symptoms of respiratory disorders by improving a patient's respiratory status by enhancing mucus clearance, reducing airway resistance, enhancing gas exchange, and reducing overall work of breathing. Chest physiotherapy and airway clearance has been the mainstay of treatment and prevention of exacerbation in the cystic fibrosis (CF) population for decades, and has had its use expanded to the non-CF bronchiectasis and acute bronchiolitis populations, and in patients being mechanically ventilated. There have also been recent positive trials within the realm of chronic bronchitis and COPD as well which showed that airway clearance was beneficial in reducing the daily volume of sputum produced and increasing FEV₁.

There have been several small studies done to analyze the utility of airway clearance and its potential role in CAP. These studies have generally been small and have used a wide variety of airway clearance devices and techniques, including external chest wall physiotherapy devices and postural drainage, both now considered second line therapies for most patients. These studies have been variable in their findings and overall have not shown that airway clearance is either beneficial or harmful in CAP. The studies did show, however, that the duration of fever and hospital length of stay were both significantly decreased, suggesting the possibility of other clinically important benefits.(Ntoumenopoulos 2002; Tydeman 1989).

Objectives:

We will test our hypothesis that the use of oPEP devices, specifically the handheld Aerobika (Monaghan Medical) in this study, will result in more rapid and durable recovery in patients hospitalized with community-acquired pneumonia as measured by decreased hospital length of stay, reduced duration of fever, improvement in dyspnea, decreased duration of antibiotics, increased rate of diagnosis of the etiologic organism responsible for the pneumonia, and reduced readmission rates:

Primary outcome

1. Reduction in hospital length of stay

Secondary outcomes

1. Reduction in dyspnea by modified-Borg score
2. Reduction in duration of antibiotics
3. Reduction in duration of fever
4. Reduction in need for oxygen at hospital discharge
5. Reduction in 30-, 60-, and 90-day readmission rates
6. Diagnosis of organism by sputum
7. Transfer to the intensive care unit (ICU)

Study type: Prospective randomized controlled trial**Design:**

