The study investigators will perform daily screening by chart review of patients admitted to the hospital in the previous 24 hours using the ICD-10 codes as below to find appropriate patients for secondary screening:

J13 Pneumonia due to Streptococcus pneumoniae

J14 Pneumonia due to Hemophilus influenzae

J15 Bacterial pneumonia, not elsewhere classified

J16 Pneumonia due to other infectious organisms, not elsewhere classified

J17 Pneumonia in diseases classified elsewhere

J18 Pneumonia, unspecified organism

J69 Pneumonitis due to inhalation of food and vomit

A partial HIPAA waiver will be obtained for the purposes of focused screening for eligibility. If the patient is deemed eligible for the study, the study investigators will approach the hospitalist/teaching attending for collateral information and permission to approach the patient for consent. After consent is obtained, the study investigator will perform a brief patient interview to obtain information on race/ethnicity, smoking and alcohol history, to confirm past medical and medication histories, and to perform baseline assessments of dyspnea (modified BORG).

Once consent is obtained, Patients will then be randomized using block randomization. We will receive pre-made envelopes in blocks of 10 from a centralized research coordinator. Investigators performing the initial screening and enrollment will be blinded to the envelope contents until after the patient consents to participation in the study. Once the patient consents to participation, the next consecutively numbered envelope will be opened revealing the allocation to either the control or intervention group. The principal investigator will keep the envelopes secured, and will be responsible for providing each envelope to the enrolling investigator after consent has been obtained.

The intervention will consist of oPEP therapy added to standard pneumonia care (see below). "Standard pneumonia care" will not be dictated by the study protocol, but rather at the discretion of the treating clinicians. Patients who are initially admitted to the intensive care unit (ICU) will not be included in this study even when they are downgraded to general medical floors, but patients will not be excluded if they are enrolled while on the medical floors and are later upgraded to ICU level of care. Enrollment will occur Monday through Friday, thus including patients being admitted on Sunday through Friday.

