Patients in the intervention group will be directed to perform the Aerobika therapy twice daily under the guidance of a study investigator for a total of at least 5 minutes per session. The study investigator will appropriately adjust the device on first use, as well as teaching the patient the correct technique for device usage. The primary patient-centered outcome will be the modified-Borg score for dyspnea which will be collected on admission, and on each subsequent morning until discharge on all enrolled patients. Patients will be encouraged to use the device on their own between the monitored sessions, as the device can safely be used multiple times daily. Patients will be surveyed each morning to self-report additional usage of the device. The device will also be available in the patient's room for in-line use of nebulizer treatments

administered by respiratory therapists, at the discretion of the therapist. Ordering of any nebulized medications is at the discretion of the treating clinicians or respiratory therapists, the latter through a standard and general respiratory therapist-driven protocol used in our institution. Charting of any nebulizer therapy will be reviewed to assess additional use of the device as well. The intervention will continue through the duration of the patient's hospitalization, and the patient will have the option to take the device at home with them if they wish to continue using it after discharge. If patients experience intolerable dyspnea or chest tightness during use of the Aerobika, despite coaching and troubleshooting by the bedside investigator, the Aerobika session will be aborted. If the patient is unable to tolerate the therapy during three consecutive sessions, then the patient will be withdrawn from intervention.

Crossover into the Aerobika group will not be restricted if the attending physician treating the patient deems it a necessary part of the patient's care. Rates of crossover will be collected as part of study data. All analyses will be performed using intention-to-treat as well as a modified intention-to-treat method considering the intervention group to include patients randomized to intervention AND who received at least one Aerobika treatment.

Variables to be collected

Demographics: Age at admission Gender Race/ethnicity (self-reported)	Lifestyle: Smoking history (ever/current/never) Alcohol consumption frequency

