Home and inpatient medications: PPI/H2-blockers Statins? Hypoglycemics/insulin Systemic steroids Inhaled medications including by nebulization Immunosuppressives	Symptoms:

Physical/Vital signs: BMI (height/weight at admission) Heart rate (daily maximum/minimum) Pulse oximetry (daily maximum/minimum, including FiO2 maximum/minimum) Temperature (daily maximum/minimum) Blood pressure (daily maximum/minimum)	Comorbidities/Past Medical History : CVA Heart disease Renal failure Cancer, active in last 6 months or not (excluding non-melanoma skin cancers) Lung disease (ie. asthma, COPD, ILD, bronchiectasis) GERD Oropharyngeal or other dysphagia
Scores: PSI - pneumonia severity index CURB65 Subjective (cough, dyspnea, mucus production) Modified-Borg score for dyspnea	

Sample size calculations

The median hospital length of stay (LOS) for Norwalk Hospital based on FY2017 data was 4.6 days (SD 3.16 days) for patients coded with a primary diagnosis of pneumonia. We will employ an effect size of 25%, powering for a reduction in LOS by 1 day.

**Two independent study groups
The primary endpoint is an average LOS (continuous variable).**

Sample Size
 Group 1 119
 Group 2 119
 Total 238

Study Parameters
 Mean LOS, group 1 4.6
 Mean LOS, group 2 3.45

Patient identity will be protected through the use of the EHR, as well as by saving abstracted PHI on a password-protected, data-encrypted, secured drive managed by information

technology (IT) at Norwalk Hospital. Additional considerations include the use of REDCap, a secured research platform, for primary data collection and storage. Data will be destroyed when all analyses and publications have been completed.

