10. Pre-existing medical condition with a life expectancy of less than 3 months
11. Inability to form appropriate mouth seal on device (eg. due to neuromuscular disease)
12. Pre-existing active use of oPEP devices
13. Requiring $\geq 50\%$ FiO₂ or facemask (excluding high flow NC)

Assessment of Efficacy:

This study is not designed to assess the efficacy of any drug, supplement, device, etc.

Assessment of Safety:

No known safety issues exist as no procedures will be conducted on patients for this study outside of the scope of their current use. Furthermore all medical devices in this study are FDA approved and currently being used for the indication being studied in this project.

Statistical Analysis:

Comparative statistics will be employed to determine if outcomes in the intervention (oPEP) group are statistically different from those in the control group. This will be done with the assistance of in-network statisticians as well as available statistical software.

Direct Access to Source Data Documents:

The study's Principal Investigator, primary study coordinator, and co-investigators will have access to all study data. These data will be used for study purposes only, and will be stored on a password-protected, data-encrypted, secure drive managed by IT at Norwalk Hospital. Data may be released to regulatory agencies as necessary, including the US Food and Drug

Administration, Department of Health and Human Services agencies, BRANY, the WCHN IRB, accrediting agencies, and data safety monitoring boards.

References:

2. Diana Tydeman (1989) An investigation into the effectiveness of physiotherapy in the treatment of patients with community-acquired pneumonia, *Physiotherapy Practice*, 5:2, 75-81, DOI: 10.3109/09593988909044416

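### Severity scores are collected but have no role in the length-of-stay analysis; adjusting for one score fixed before allocation could narrow the interval at little cost

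*Combined protocol and SAP*

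**What the plan says.** The analysis plan for all outcomes is essentially one sentence in Statistical Analysis: "Comparative statistics will be employed to determine if outcomes in the intervention (oPEP) group are statistically different from those in the control group". What follows it refers only to statisticians and software. The Design section adds the analysis sets: "All analyses will be performed using intention-to-treat as well as a modified intention-to-treat method". Sample size calculations describes the endpoint as "The primary endpoint is an average LOS (continuous variable" and gives means of 4.6 and 3.45 days, SD 3.16 and 119 patients per group.

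The list under Variables to be collected includes "PSI - pneumonia severity index CURB65 Subjective (cough, dyspnea, mucus production) Modified-Borg score for dyspnea". PSI and CURB65 appear nowhere else, and no time point is given for them. Modified Borg is a secondary outcome in Objectives ("Reduction in dyspnea by modified-Borg score"). Design says of it "The primary patient-centered outcome will be the modified-Borg score for dyspnea which will be collected on admission", with repeat scores each morning until discharge. The interview after consent is also used "to perform baseline assessments of dyspnea (modified BORG". Randomisation is in blocks of 10, and no strata are stated.

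**The concern.** Length of stay varies widely between patients: the plan's SD is 3.16 days against a target difference of 1.15. If a severity score fixed before allocation predicts part of that variation, including it in the model narrows the interval for the treatment difference with the same 238 patients. The plan collects candidate scores and gives them no such role.

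Margin may be short. The text speaks of a one-day reduction while the means entered differ by 1.15 days, and under the plan's single SD the power for 1.0 day is about 68%. Naming the model and the score in advance also stops either from being chosen after the outcomes are seen.

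**Working it through.** **Inputs from Sample size calculations:** SD 3.16; means 4.6 and 3.45 (difference 1.15, which is 25% of 4.6); a stated reduction of 1 day; 119 per group. **Inferred:** two-sided 0.05 and 80% power, neither of which is stated. **Assumed:** R2 of 0.02, 0.10 or 0.30 between the score and length of stay, because the documents give no value.

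**1. The plan's own figure.** n per group = 2 × (3.16 × (1.960 + 0.842) / 1.15)² = 118.5, so 119. It reproduces with no covariate and no allowance for dropout.

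**2. Interval width, constant SD.** Residual SD = 3.16 × √(1 − R2). Half-width = t(0.975, 236 df) × residual SD × √(2/119). Equivalent unadjusted n per arm = 119 / (1 − R2).

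| R2 | 95% CI half-width (days) | Equivalent n per arm |
|---|---|---|
| 0 | 0.807 | 119 |
| 0.02 | 0.799 | 121 |
| 0.10 | 0.766 | 132 |
| 0.30 | 0.675 | 170 |

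**3. Power if 4.6 is a mean.** Noncentral t, 119 per arm. Under a proportional effect the treated-arm SD shrinks to 3.16 × (4.6 − d) / 4.6, which is 2.47 at d = 1.0 and 2.37 at d = 1.15 (Welch degrees of freedom).

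| Setting | R2 0 | 0.02 | 0.10 | 0.30 |
|---|---|---|---|---|
| Constant SD, 1.0 day | 0.681 | 0.690 | 0.727 | 0.828 |
| Constant SD, 1.15 days | 0.798 | 0.806 | 0.838 | 0.916 |
| Proportional, 1.0 day | 0.772 | 0.781 | 0.814 | 0.899 |
| Proportional, 1.15 days | 0.885 | 0.891 | 0.915 | 0.966 |

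Simulations with skewed data (lognormal and gamma, control mean 4.6 and SD 3.16, 10,000 runs per setting) compared a Welch t test with a linear model in days using HC3 robust errors. For example, with a lognormal shift of 1.0 day, power went from 0.695 to 0.727 at R2 0.10 and from 0.683 to 0.822 at R2 0.30. Adjusted type I error was 0.045 to 0.050 in all six null settings. Over the table and the simulations together, the gain is about 0-1 point at R2 0.02, 2-5 at 0.10 and 7-15 at 0.30.

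**4. Power if 4.6 is a median.** The same section first calls 4.6 the median. For a lognormal with median 4.6 and SD 3.16, let x = exp(σ²). Then 4.6² × x(x − 1) = 3.16², so x = 1.350 and the mean is 4.6 × √1.350 = 5.34. A proportional 25% effect is then 1.34 days, with treated-arm SD 0.75 × 3.16 = 2.37. SE = √((3.16² + 2.37²)/119) = 0.362. Power is 0.957 unadjusted and 0.960, 0.972 or 0.992 at R2 0.02, 0.10 or 0.30: gains of about 0.3, 1.5 and 3.6 points.

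**5. Timing.** Design says "The study investigators will perform daily screening by chart review of patients admitted to the hospital in the previous 24 hours", so patients are already admitted when found, and admission chart data should precede allocation. Vital signs, however, are recorded as daily maxima and minima, and a first-day extreme can fall after allocation. The order of the text suggests that the baseline Borg comes before the envelope, but no sentence says so.

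**The case against.** An unadjusted comparison in a 1:1 randomised trial is valid, so adjustment is an efficiency choice. No document links any of these scores to length of stay, so R2 could be near zero. The design also narrows the severity range: it leaves out patients first admitted to the ICU, haemodynamically unstable patients, and those on at least 50% oxygen or a facemask. That tends to lower the R2 of a severity score. Other uncertainties are larger: at 1.0 day, moving from constant SD to a proportional effect changes unadjusted power by about 9 points (0.681 to 0.772), more than adjustment at R2 0.10 does. All of this stands, and it limits the size of the claim. It does not remove the case for a low-cost change.

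A reader might infer three stronger things that the documents do not support:
- That the plan commits to an unadjusted analysis. It does not: the wording could cover a regression model, and the sizing does not exclude one. No adjusted analysis is planned, which is a weaker statement.
- That leaving out the scores would bias the result. Randomisation protects against that; only precision is at issue.
- That a particular power gain is available. Every power figure depends on an assumed R2 and on whether 4.6 is a mean or a median, and the section calls it both.

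**Conclusion.** The point holds as a worthwhile improvement, not as an error that invalidates the trial. Scores are collected with no covariate or stratification role, and the sizing takes no credit for them.

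With constant SD, the interval half-width falls from 0.81 to 0.80, 0.77 or 0.68 days at R2 0.02, 0.10 or 0.30. The power gain ranges from almost nothing to about 15 points if 4.6 is a mean, and to about 3.6 points if it is a lognormal median with a proportional 25% effect. These figures rest on the inferred two-sided 0.05, full follow-up of 119 per arm and the assumed R2 values. Confidence is high that no covariate role is stated and moderate at best on the size of the benefit.

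**What to change.** Before any outcome data are seen, write into the Statistical Analysis section:

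- **Primary analysis.** A linear model of length of stay in days on arm plus one named severity score (for example continuous PSI), with robust standard errors. Report the adjusted mean difference with its 95% CI, and the unadjusted difference as a sensitivity analysis.
- **Score definition.** Build the score only from chart data time-stamped before randomisation, not from daily maxima or minima that may fall after it. It may be calculated later from the chart.
- **Missing score.** Use a rule that ignores arm, such as imputing the overall mean.
- **Modified Borg.** State that the baseline is taken before the envelope is opened, and use it as a covariate. Name the outcome day or summary, because daily scores stop at discharge and so depend on length of stay, the primary outcome.

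The cost is mainly SAP wording, with no added patients, visits or measurements. It assumes that the chart holds time-stamped score components, which is plausible for patients already admitted but is not stated. The target stays a mean difference in days, so the plan should also settle whether 4.6 is a mean or a median. The downside is a gain close to nil if the chosen score explains little of length of stay.

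### The plan does not say whether or how the baseline modified-Borg score enters the dyspnea comparison, and both natural readings of the outcome are no more precise than adjusting for it

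*Combined protocol and SAP*

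**What the plan says.** Four places in the combined protocol and SAP bear on this.

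- **Objectives.** The first secondary outcome is "Reduction in dyspnea by modified-Borg score", and the hypothesis speaks of "improvement in dyspnea". Neither phrase is defined as a level at a given time or as a change from the patient's own starting value.
- **Design, consent and randomization.** After consent the investigator holds a short interview, among other things "to perform baseline assessments of dyspnea (modified BORG". The next paragraph says "Patients will then be randomized using block randomization". Envelopes come in blocks of 10, and no stratification is mentioned.
- **Design, intervention.** "The primary patient-centered outcome will be the modified-Borg score for dyspnea which will be collected on admission, and on each subsequent morning until discharge". This applies to all enrolled patients.
- **Statistical Analysis.** The method for every outcome is one sentence: "Comparative statistics will be employed to determine if outcomes in the intervention (oPEP) group are statistically different from those in the control group". No test, model, covariate or time point is named. The only other analysis detail, in the Design section, is that intention-to-treat and modified intention-to-treat sets will be used.

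**The concern.** A patient's own starting score is usually among the better predictors of later scores on the same scale, and here it is already collected. With no stated analysis, the dyspnea result could come from raw follow-up scores, from change scores or from an adjusted model, and the choice could be made after the data are seen.

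The three analyses differ in precision. They also respond differently to a chance difference between the arms at baseline. A raw comparison then favours the arm that began less breathless, and a change-score comparison favours the arm that began more breathless. At stake is the power and interpretability of the outcome that the protocol singles out as its main patient-centered one.

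**Working it through.** **The plan's own figure.** The documents give a sample size for length of stay only: 119 per group, from means of 4.6 and 3.45 days and an SD of 3.16. Alpha and power are not stated. Assuming two-sided 0.05 and 80%:

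n = 2 × (1.960 + 0.842)² × 3.16² / 1.15² = 118.5, rounded up to 119 per group.

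The stated figure is reproduced. Nothing below disputes it; 119 per arm is carried over to dyspnea.

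**Assumptions for dyspnea.** The documents give no Borg SD, no correlation r between baseline and follow-up, and no power. I work in SD units, take r = 0.3, 0.5 and 0.7, assume equal SDs at baseline and follow-up, one follow-up score per patient, and all 119 per arm observed.

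**Variance relative to a raw follow-up comparison.**
- Raw: 1
- Change score: 2(1 − r)
- ANCOVA on baseline: 1 − r²

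The change score exceeds ANCOVA by 2(1 − r) − (1 − r²) = (1 − r)², and raw exceeds ANCOVA by r². Both are positive for any r strictly between 0 and 1, so in that range ANCOVA has the smallest variance of the three.

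**Power.** Set the true effect so that the raw comparison has 80% power: 2.802 × √(2/119) = 0.363 SD. Then power = Φ(2.802/√V − 1.96), where V is the relative variance.

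| r | V, ANCOVA | Power, ANCOVA | V, change | Power, change | Difference detectable at 80%, ANCOVA |
|---|---|---|---|---|---|
| 0.3 | 0.91 | 83.6% | 1.40 | 65.8% | 0.346 SD |
| 0.5 | 0.75 | 89.9% | 1.00 | 80.0% | 0.315 SD |
| 0.7 | 0.51 | 97.5% | 0.60 | 95.1% | 0.259 SD |

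The variance saving against raw scores (9%, 25%, 51%) is what an unadjusted trial would need about 119/V = 131, 159 or 233 per arm to match.

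**Chance imbalance.** The standard error of the baseline difference is √(2/119) = 0.130 SD, so 95% of randomizations give a difference within 1.96 × 0.130 = 0.25 SD. At that limit:
- A raw comparison is shifted by r × 0.254 = 0.08, 0.13 or 0.18 SD.
- A change-score comparison is shifted the other way by (1 − r) × 0.254 = 0.18, 0.13 or 0.08 SD.
- The type I error of the raw test, conditional on that imbalance, is 1 − Φ(1.96(1 − r)/√(1 − r²)) + Φ(−1.96(1 + r)/√(1 − r²)), or about 8%, 13% or 21%.

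Averaged over all randomizations it is 5%.

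**The case against.** The strongest reply is that silence is not a decision. A reader might infer that the trial has chosen to ignore the baseline score. The documents do not support that. The Statistical Analysis section names no method for any outcome and leaves the work to statisticians in the hospital's network. The outcome wording also allows change from baseline, which does use each patient's own starting score. This stands: the fault is a missing commitment, not a wrong analysis.

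A reader might also infer that an unadjusted dyspnea comparison would be biased because allocation is not stratified. That does not follow. Randomization balances baseline dyspnea in expectation and the error rate holds on average; the distortion is conditional on an imbalance that may not occur.

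Three further objections have force:
- The size rests wholly on an assumed correlation. At r = 0.3 the gain over raw scores is under 5 points, and at r = 0.7 the gain over a change score is about 2 points.
- Equal SDs may not hold in patients who are recovering, and the formulas describe a single fully observed follow-up score rather than a repeated-measures model.
- Dyspnea is a secondary outcome. The label of primary patient-centered outcome does not displace length of stay, which the Objectives and the sample size calculation treat as primary.

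These limit the size of the point. They do not remove it, because neither natural reading of the outcome is more precise than the adjusted analysis at any of the correlations considered.

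**Conclusion.** The point holds as a gap in specification with a concrete and nearly free improvement. The baseline score is collected, nothing commits the trial to using it, and both natural readings of the outcome are no more precise than baseline adjustment. Where a raw comparison has 80% power, adjustment gives about 84% to 98% and a change score 66% to 95% over r = 0.3 to 0.7, under the assumptions listed with the calculation. The real gain is unknown because the documents give no correlation.

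The loss is precision, with conditional bias if the arms happen to differ at baseline. It is not a loss of validity on average, and it does not touch the length-of-stay analysis or its sample size.

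Two related gaps limit any dyspnea analysis. First, the baseline is described in two ways. One Design paragraph places it at the interview after consent; the other says "The primary patient-centered outcome will be the modified-Borg score for dyspnea which will be collected on admission". The order of text suggests that the interview comes before the envelope is opened, but both steps are tied to consent and the order is not explicit. Second, scores stop at discharge. The trial's hypothesis is that the device shortens the stay, so which mornings are observed may depend on treatment.

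**What to change.** In Statistical Analysis, state that the modified-Borg comparison between arms includes baseline modified-Borg as a covariate, in one of two forms:

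- ANCOVA on the score at one named early morning; or
- a repeated-measures model on the morning scores over a fixed early window.

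In Design, define the baseline as the score taken after consent and before first use of the device, and reconcile the interview paragraph with the one that places the first score at admission.

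This takes a few sentences and no new data, visits, staff or patients. The costs are one model parameter and the need to name the time point or window now. An early time point limits the number of patients already discharged, but baseline adjustment does not by itself solve scores ending at discharge, so the plan should also say how those patients are handled.
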